9.3.2. Outcomes

All outcomes will be assessed starting on Day 15. All hospitalization related outcomes in the table below will be ascertained using acute facility stays only. Inpatient stays classified as skilled nursing facility or rehabilitation will not be used. COVID-19 and flu hospitalizations will be assessed in any position and in the primary position to mitigate possibility of hospitalization with the disease versus for the disease.

COVID-19 related endpoints will be identified using the following ICD-10-CM diagnosis code: U07.1.

Influenza will be identified using the following ICD-10-CM diagnosis codes: J09.X, J10.X, J11.X.

We will evaluate three negative control outcomes. These outcomes are unrelated to vaccination and likely share similar confounding patterns for health-seeking behaviors. These negative controls have been used in other studies of comparative VE of influenza vaccines or COVID-19 VE.¹³⁻¹⁵ Urinary tract infection and accidental injury are outcomes that could differentiate patients who seek medical care versus those who do not, and is likely a better choice of outcome for younger adults. Hospitalization in the first 14 days (ie, among recently vaccinated) uses time as a negative control, in that the vaccine likely could not biologically prevent health events until adequate levels of immunity has been achieved.

Table 2. Outcome Variables

Variable	Role	Operational definition
All-cause hospitalization	Outcome	An inpatient (acute facility) claim that meets the following criteria: 
1. Occurs >14 days after the patient's first mRNA bivalent COVID-19 or influenza vaccine dose during the study period.2. Place of service = 21.3. Non-null confinement ID.4. tos_cd = 'FAC_IP.ACUTE'.
Composite COVID-19 related hospitalization/ED/UC (any position)	Outcome	An inpatient (acute facility) claim that meets the following criteria: 
1. Occurs >14 days after the patient's first mRNA bivalent COVID-19 or influenza vaccine dose during the study period.2. Place of service = 21.

PFIZER CONFIDENTIAL

Table 2. Outcome Variables

Variable	Role	Operational definition
		
3. Non-null confinement ID.
 
4. tos_cd = 'FAC_IP.ACUTE'.
 
5. COVID-19 diagnosis code (ICD-10-CM: U07.1) in any position
 
OR
 
An ED/urgent care claim that meets the following criteria:
 
 1. Occurs >14 days after the patient's first mRNA bivalent COVID-19 or influenza vaccine dose during the study period. 2. Place of service = 23 or 20. 3. Confinement id = null. 4. COVID-19 diagnosis code (ICD-10-CM: U07.1) in any position
COVID-19 related hospitalization (any position)	Outcome	
An inpatient (acute facility) claim that meets the following criteria:
 
 1. Occurs >14 days after the patient's first mRNA bivalent COVID-19 or influenza vaccine dose during the study period. 2. Place of service = 21. 3. Non-null confinement ID. 4. tos_cd = 'FAC_IP.ACUTE'. 5. COVID-19 diagnosis code (ICD-10-CM: U07.1) in any position.
CCI		
[REDACTED]
 
[REDACTED]
 
[REDACTED]
 
[REDACTED]

[figure not shown]
[figure not shown]
[figure not shown]
[figure not shown]
[figure not shown]
[figure not shown]
[figure not shown]
[figure not shown]
[figure not shown]
[figure not shown]
[figure not shown]
[figure not shown]
[figure not shown]
[figure not shown]
[figure not shown]
[figure not shown]
[figure not shown]
[figure not shown]
[figure not shown]
[figure not shown]
[figure not shown]
[figure not shown]
[figure not shown]
[figure not shown]
[figure not shown]
[figure not shown]
[figure not shown]
[figure not shown]
PFIZER CONFIDENTIAL

Table 2. Outcome Variables

Variable	Role	Operational definition
		
cc1 [REDACTED] [REDACTED] [REDACTED]

Composite influenza-related hospitalization/ED/UC (any position)		
An inpatient (acute facility) claim that meets the following criteria:
 
 1. Occurs >14 days after the patient's first mRNA bivalent COVID-19 or influenza vaccine dose during the study period. 2. Place of service = 21. 3. Non-null confinement ID. 4. tos_cd = 'FAC_IP.ACUTE' 5. Influenza diagnosis code (ICD-10-CM: J09.X, J10.X, J11.X) in any position. 
OR
 
An ED/urgent care claim that meets the following criteria:
 
 1. Occurs >14 days after the patient's first mRNA bivalent COVID-19 or influenza vaccine dose during the study period. 2. Place of service = 23 or 20. 3. Confinement id = null. 4. Influenza diagnosis code (ICD-10-CM: J09.X, J10.X, J11.X) in any position.
Influenza-related hospitalization (any position)	Outcome	
An inpatient (acute facility) claim that meets the following criteria:
 
 1. Occurs >14 days after the patient's first mRNA bivalent COVID-19 or influenza vaccine dose during the study period. 2. Place of service = 21.

PFIZER CONFIDENTIAL

Table 2. Outcome Variables

Variable	Role	Operational definition
		
3. Non-null confinement ID.
 
4. tos_cd = 'FAC_IP.ACUTE'.
 
5. Influenza diagnosis code (ICD-10-CM: J09.X, J10.X, J11.X) in any position.

CCI		                                              
COVID-19 related ED/Urgent care visit (any position)	Outcome	
An ED/urgent care claim that meets the following criteria:
 
 1. Occurs >14 days after the patient's first mRNA bivalent COVID-19 or influenza vaccine dose during the study period. 2. Place of service = 23 or 20. 3. Confinement id = null. 4. COVID-19 diagnosis code (ICD-10-CM: U07.1) in any position.
Influenza-related ED/Urgent care visit (any position)	Outcome	
An ED/urgent care claim that meets the following criteria:
 
 1. Occurs >14 days after the patient's first mRNA bivalent COVID-19 or influenza vaccine dose during the study period. 2. Place of service = 23 or 20. 3. Confinement id = null.

PFIZER CONFIDENTIAL

Table 2. Outcome Variables

Variable	Role	Operational definition
		4. Influenza diagnosis code (ICD-10-CM: J09.X, J10.X, J11.X) in any position.
COVID-19related outpatient visit (any position)	Outcome	
An outpatient claim that meets the following criteria:
 
 1. Occurs >14 days after the patient's first mRNA bivalent COVID-19 or influenza vaccine dose during the study period. 2. Confinement id = null. 3. COVID-19 diagnosis code (ICD-10-CM: U07.1) in any position. 4. Does not meet the definition of an ED/UC/hospital visit.
Influenza-related outpatient visit (any position)	Outcome	
An outpatient claim that meets the following criteria:
 
 1. Occurs >14 days after the patient's first mRNA bivalent COVID-19 or influenza vaccine dose during the study period. 2. Confinement id = null. 3. Influenza diagnosis code (ICD-10-CM: J09.X, J10.X, J11.X) in any position. 4. Does not meet the definition of an ED/UC/hospital visit.
Urinary tract infection	Negative control outcome	≥1 ICD-10-CM diagnosis code in any position/any setting for a urinary tract infection (that occurs >14 days after the patient's first mRNA bivalent COVID-19 or influenza vaccine dose during the study period).
Accidental injury	Negative control outcome	≥1 ICD-10-CM diagnosis code in any position/any setting for accidental injury that occurs >14 days after the patient's first mRNA bivalent COVID-19 or influenza vaccine dose during the study period.
Hospitalization in the 14 days following vaccination (recently vaccinated) Day 1-14	Negative control outcome	
An inpatient (acute facility) claim that meets the following criteria:
 
 1. Occurs ≤14 days after the patient's first mRNA bivalent COVID-19 or influenza vaccine dose during the study period.

PFIZER CONFIDENTIAL

Table 2. Outcome Variables

Variable	Role	Operational definition
		2. Place of service = 21. 3. Non-null confinement ID.
CCI		
CCI		
CCI		
CCI		

PFIZER CONFIDENTIAL

Table 2. Outcome Variables

Variable	Role	Operational definition
		within 60 days following discharge.
CCI [REDACTED]	[REDACTED]	[REDACTED]
Follow-up time	Outcome descriptive	Measured from day 15 through the minimum date of censoring (see follow-up time description in Section 9.3.3). Mean, standard deviation (SD), median (Q1-Q3), minimum, and maximum, will also be summarized for the length of follow-up in each group.

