7. RATIONALE AND BACKGROUND

Data suggest severe acute respiratory syndrome coronavirus 2 (SARS-CoV-2) likely follows a seasonality pattern as with other respiratory viral infections such as influenza; where activity peaks during the traditional winter viral respiratory season.¹ CDC guidance for the 2020 and 2021 flu seasons included a recommended time interval of at least 14 days between flu and COVID-19 vaccines.² Based on updated data, the CDC has revised their recommendations that COVID-19 vaccines may be co-administered with seasonal influenza vaccines (SIV).³ Specifically, COVID-19 and SIV can be administered concomitantly, and routine administration of all age-appropriate doses of vaccines simultaneously is recommended for children, adolescents, and adults.³ A systematic literature review of 30 studies revealed that when SIV and COVID-19 booster vaccines are combined, there is potential for an increase in the uptake of the COVID-19 vaccine, predominately because many individuals are accustomed to taking SIV annually.⁴

Studies have reported similar safety and immunogenicity among those who received co-administered COVID-19 vaccine and SIV compared to those who received these vaccines separately.⁵⁻¹¹ Three of these studies were clinical trials comparing safety and immunogenicity between SIV and COVID-19 co-administration versus SIV or COVID-19 alone. In these three clinical trials, no safety concerns or immune interferences were found regardless of the vaccines or the age of vaccinated subjects (18-64 or 65+).^{6,9-11} Hause et al in a retrospective cohort study of self-reported vaccine data found a significant increase in reports of systemic reactions 0-7 days following co-administration of a COVID-19 mRNA booster vaccines with an SIV compared to COVID-19 mRNA vaccine alone;⁵ whereas results from a VAERS database⁸ and the National Health Interview Survey⁷ analyses found no unusual or unexpected patterns of AEs or differences in symptom severity.

Regarding efficacy/effectiveness, one study was identified and reviewed. Novavax's NVX-CoV2373 COVID-19 vaccine efficacy when co-administered with the quadrivalent influenza cell-based vaccine Flucelvax (Seqirus UK, Maidenhead) among individuals aged 18 to <65 years was 87.5% (95% CI -0.2 to 98.4); was slightly attenuated compared to when administered alone (89.8% (95% CI 79.7-95.5).⁹

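### The rationale for the Day 1-14 hospitalization control rules out early benefit but not early harm; splitting the window at Day 7 would help tell an early reaction effect from confounding

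*Combined protocol and SAP*

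**What the plan says.** Section 9.3.2 states: "We will evaluate three negative control outcomes". They are urinary tract infection, accidental injury and hospitalization in the first two weeks. It says of all three, without qualification: "These outcomes are unrelated to vaccination and likely share similar confounding patterns for health-seeking behaviors". The specific reason for the third is that "the vaccine likely could not biologically prevent health events until adequate levels of immunity has been achieved".

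In Table 2 the row is "Hospitalization in the 14 days following vaccination (recently vaccinated) Day 1-14". It counts an acute-facility inpatient claim up to 14 days after the first vaccine dose, with no restriction on diagnosis.

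Section 7 cites a "retrospective cohort study of self-reported vaccine data" that "found a significant increase in reports of systemic reactions 0-7 days following co-administration of a COVID-19 mRNA booster vaccines with an SIV", the comparison being COVID-19 mRNA vaccine alone. The same paragraph also reports three clinical trials in which "no safety concerns or immune interferences were found regardless of the vaccines or the age of vaccinated subjects", and says that VAERS and National Health Interview Survey "analyses found no unusual or unexpected patterns of AEs or differences in symptom severity".

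The readable text of Section 9.7 does not list the negative controls among the models and gives no rule for interpreting a difference on them. A redacted block follows that list.

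**The concern.** A negative control outcome is useful only if the exposure contrast cannot affect it in either direction. Here the contrast is two vaccines together against one alone. The plan argues that vaccination cannot yet prevent admissions in the first two weeks. It does not consider whether vaccination could cause some, although its own background reports a reaction difference in the first week for co-administration against COVID-19 vaccine alone.

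If reactions did lead to some admissions, a Group 1 excess in this control would have two possible explanations, and the 14-day total could not separate them. If same-day recipients were also healthier, the two influences would pull in opposite directions, and the control could look closer to null than the confounding alone would make it. Either way, a check meant to reveal bias in the effectiveness estimates becomes harder to read.

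**Working it through.** The plan gives no figure on this point, so the check is a comparison of texts followed by an illustration.

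**1. What the control needs and what the plan supplies**

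| Requirement | Support in the plan |
|---|---|
| No early benefit | Stated as the rationale in Section 9.3.2 |
| No early harm | Not addressed in Section 9.3.2; evidence in Section 7 is mixed |
| Reaction-related admissions kept out | No: Table 2 sets no cause restriction, and exclusion criterion 4 (Section 9.2.2) removes only patients with COVID-19 or influenza codes |

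The day 0-7 window of the cited study covers Days 1-7 of the control, that is 7/14 = 50% of it.

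**2. What one window can show**

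Let c be the hazard ratio due to confounding and x the proportional excess of admissions on Days 1-7 caused by co-administration. Both are assumed. With the same baseline admission rate every day:

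- Days 1-7: HR = c(1 + x)
- Days 8-14: HR = c
- Days 1-14: HR = c[0.5(1 + x) + 0.5] = c(1 + x/2)

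| c | x | Days 1-7 | Days 8-14 | Days 1-14 |
|---|---|---|---|---|
| 1.05 | 0 | 1.05 | 1.05 | 1.05 |
| 1.00 | 10% | 1.10 | 1.00 | 1.05 |
| 1.00 | 20% | 1.20 | 1.00 | 1.10 |
| 0.95 | 10% | 1.045 | 0.95 | 0.998 |
| 0.95 | 20% | 1.14 | 0.95 | 1.045 |
| 0.90 | 10% | 0.99 | 0.90 | 0.945 |
| 0.90 | 20% | 1.08 | 0.90 | 0.99 |

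The first two rows give the same 14-day result from opposite causes. The last four show confounding that is offset in full or in part. In every row the Days 8-14 column returns c, provided there is no effect after Day 7.

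**3. How small an excess would register, Group 1 vs Group 2**

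Group sizes are from Table 5: 382,806 and 225,842 (65+); 244,864 and 144,695 (18-64). The documents give no Day 1-14 admission risk, so the comparator risk is assumed to lie between 0.05% and 1.0%. The 95% interval of an unweighted risk ratio excludes 1 when ln(RR) > 1.96 × √(1/d1 + 1/d2), where d1 and d2 are the event counts.

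Example, 65+ at 1.0%: an excess of 5.29 per 10,000 gives d1 = 382,806 × 0.010529 ≈ 4,031 and d2 ≈ 2,258. The standard error is 0.0263, so the threshold is 1.96 × 0.0263 = 0.0515, which equals ln(1.0529).

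Across the assumed range:

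- 65+: 1.25 per 10,000 (RR 1.251, at 0.05%) to 5.29 per 10,000 (RR 1.053, at 1.0%)
- 18-64: 1.60 per 10,000 (RR 1.320) to 6.63 per 10,000 (RR 1.066)

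**4. What a split costs in precision**

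If events are spread evenly, each half-window has half the risk, and the standard error grows by about √2 = 1.41. The smallest RR whose interval excludes 1 then changes as follows:

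| Assumed 14-day comparator risk | Age | 14 days | 7 days |
|---|---|---|---|
| 1.0% | 65+ | 1.053 | 1.075 |
| 1.0% | 18-64 | 1.066 | 1.095 |
| 0.1% | 65+ | 1.173 | 1.251 |
| 0.1% | 18-64 | 1.220 | 1.320 |

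**The case against.** The case against is substantial, and most of it limits the size of the point.

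- **Reactions are not admissions.** The one positive signal is self-reported systemic reactions. Nothing in the documents says that they lead to hospital stays, and the 10-20% excess above is an assumption. This stands.
- **The other evidence is reassuring.** The trials, VAERS and survey findings sit in the same paragraph and must be weighed with the signal. This stands.
- **The contrast matches only in part.** Section 7 reports the signal against COVID-19 vaccine alone, so it gives no support for Group 1 vs Group 3. The reference list places the study in issue 7 of a 2022 volume, while Section 9.2 dates the bivalent authorization to 31 August 2022, so the study appears to concern an earlier booster. This stands.
- **No misreading is written into the plan.** A reader might infer that the sponsor will label any Group 1 excess as confounding. That follows only from the term negative control; no readable rule says so, and relevant text may be redacted.
- **Two other controls remain.** Urinary tract infection and accidental injury are unaffected. A Day 1-14 difference with both of those null would itself argue against general care-seeking bias.
- **Masking is partial.** With c = 0.90 and x = 10%, the 14-day value of 0.945 still points in the direction of the bias.
- **Day 7 is one study's reporting limit, not a proven end of effect.** Calling Days 8-14 free of any vaccine effect would repeat the same overstatement. This stands, so the fix has to state the assumption rather than assert it.

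None of this supplies the missing half of the rationale: Section 9.3.2 still makes an unqualified statement that its reasoning supports in one direction only.

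**Conclusion.** The point holds as a cheap improvement. For Day 1-14 hospitalization in Group 1 vs Group 2, the assumption of no early harm is neither argued nor clearly supported by the plan's own background, and a single 14-day window could not separate an early reaction effect from confounding.

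The size is unknown. The hazard ratios of 1.05-1.10, and of 0.945-1.045 with confounding, rest on an assumed excess of 10-20% on Days 1-7, assumed confounding of 0.90-0.95 and a constant daily admission rate. The excess of 1.25 to 6.63 per 10,000 that would register rests on assumed comparator risks of 0.05% to 1.0% and ignores weighting. It shows that the control is sensitive, not that such an excess exists.

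A reader might infer that co-administration raises admissions, that the control is invalid, or that the effectiveness results are biased. The documents support none of these. Nor is it a defect that the effectiveness outcomes, which start on Day 15, leave out early reactions: the objectives in Section 8 are uptake and effectiveness, not safety.

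**What to change.** 1. In Table 2, keep the Day 1-14 hospitalization row and add two rows with the same claim definition: Days 1-7 and Days 8-14.
2. Name Days 8-14 as the main time-based negative control. State in advance that a Days 1-7 difference may reflect either confounding or early reactogenicity.
3. In Section 9.3.2, limit the statement that the outcomes have no link to vaccination to urinary tract infection and accidental injury. For the time-based control, say that it assumes neither early benefit nor early harm.

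The cost is one extra date cut in data already held, some rewording and slightly more analysis. Each sub-window would hold roughly half the events, so estimates would be less precise. The exact loss cannot be given, because the documents do not state a Day 1-14 admission rate. Keeping the 14-day row means that the planned result is not lost.

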9.2.2. Exclusion Criteria

Patients meeting any of the following criteria will not be included in the study:

1. Patients with a second dose of any type of bivalent mRNA COVID-19 or flu vaccine, disenrolled or died within 14 days following the first dose.
2. Has prior COVID-19 diagnosis (U07.1, any setting, any position) within 90 days (per CDC guidance¹² on length of time before receiving a vaccine) before and on index.
3. Has influenza vaccine between 01 August -30 August 2022 (before study period).

PFIZER CONFIDENTIAL

4. Has a COVID-19 or influenza diagnosis code in any setting within 14 days after index vaccination (excluded from all cohorts).
5. For patients 65+, had a standard dose influenza vaccine or unknown type influenza vaccine.
6. Has Moderna mRNA bivalent COVID-19 vaccine or monovalent vaccine of any type on index date.

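### The UTI and accidental-injury negative controls mix follow-up care for earlier episodes with new episodes, so their hazard ratios are harder to read, in a direction the documents do not settle

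*Combined protocol and SAP*

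**What the plan says.** Section 9.3.2 gives the purpose of the negative controls: "These outcomes are unrelated to vaccination and likely share similar confounding patterns for health-seeking behaviors". It adds that UTI and accidental injury "are outcomes that could differentiate patients who seek medical care versus those who do not".

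Table 2 defines the two controls in the same way. UTI is one or more "diagnosis code in any position/any setting for a urinary tract infection" after Day 14. Injury is one or more "diagnosis code in any position/any setting for accidental injury" after Day 14. The section also states: "All outcomes will be assessed starting on Day 15". Table 3 (section 9.3.3) ends follow-up at the outcome under study, so the first qualifying claim is the event.

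The exclusions in section 9.2.2 set a pre-index window for COVID-19 only: "Has prior COVID-19 diagnosis (U07.1, any setting, any position) within 90 days" before and on index. They also remove patients with a COVID-19 or influenza code in the 14 days after index. Neither exclusion covers UTI or injury.

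Table 4 (section 9.3.4) lists comorbidities and general utilisation (outpatient days, admissions, laboratory orders, telehealth visits). It lists neither prior UTI nor prior injury.

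**The concern.** A negative control is useful when its HR can be read as a measure of residual confounding. Here one HR covers two things. One is a new episode that brings the patient to care after Day 14. The other is a further claim for an episode that began before vaccination or in Days 0 to 14. Because follow-up stops at the event, a carry-over claim also hides any later new episode in the same patient.

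The two components need not carry the same between-group difference, so the blended HR may sit nearer to 1 than the HR for new episodes, equal it, or lie further away. There is a separate route to imbalance. If the index vaccine was given at a visit for the same injury or infection, follow-up claims for that condition are linked to the vaccination visit. That says little about bias in the COVID-19 or influenza endpoints. Table 4 adjusts for the place of vaccination (pharmacy, office, other) but not for the reason for the visit.

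At stake is how much reassurance, or alarm, the team may take from these two controls when it reads effect estimates against the 1.15 margin in section 9.5.

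**Working it through.** **Figures in the plan.** The documents give no event rate, power or expected HR for any negative control, so there is no stated figure to reproduce on this point. The nearest are the event counts in section 9.5 for the 65+ composites. Schoenfeld's formula (margin 1.15, one-sided alpha 0.025, power 80%) gives 1,724 events with 63% in Group 1 and 2,269 with 23%. Both match the plan, and nothing below depends on them.

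**Effect of mixing.** Inputs:
- f, the share of comparator-group control events that are carry-over: not in the documents; assumed 10%, 30%, 50%.
- HR for new episodes: assumed 0.90, and 1.15 as a second case.
- HR for carry-over claims: assumed 1 (balanced), equal to the HR for new episodes (equally confounded), or its square (more confounded).

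For rare events, observed HR ≈ (1 − f) × HR_new + f × HR_carry. For example, 0.7 × 0.90 + 0.3 × 1 = 0.93.

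| HR_new | HR_carry | f = 10% | f = 30% | f = 50% |
|---|---|---|---|---|
| 0.90 | 1 | 0.91 | 0.93 | 0.95 |
| 0.90 | 0.90 | 0.90 | 0.90 | 0.90 |
| 0.90 | 0.81 | 0.891 | 0.873 | 0.855 |
| 1.15 | 1 | 1.135 | 1.105 | 1.075 |
| 1.15 | 1.15 | 1.15 | 1.15 | 1.15 |
| 1.15 | 1.3225 | 1.167 | 1.202 | 1.236 |

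Without carry-over (f = 0) the control shows 0.90 or 1.15. The sign of the shift depends wholly on HR_carry, which the documents do not inform.

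**Would a diluted signal be missed?** Take the 65+ Group 1 vs Group 2 counts from Table 5 (382,806 and 225,842), HR_new 0.90, an assumed 1% comparator incidence of new episodes, and unweighted variance.
- f = 0: events 382,806 × 0.01 × 0.90 = 3,445 and 225,842 × 0.01 = 2,258. SE of log HR = √(1/3,445 + 1/2,258) = 0.0271. HR 0.90, 95% CI 0.853 to 0.949.
- f = 50%, balanced: the comparator rate becomes 0.01/0.5 = 2%. Events 382,806 × 0.02 × 0.95 = 7,273 and 225,842 × 0.02 = 4,517. SE = 0.0189. HR 0.95, 95% CI 0.915 to 0.986.

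The same f = 50% case at ages 18-64 (244,864 and 144,695) gives 4,652 and 2,894 events, SE 0.0237 and a 95% CI of 0.907 to 0.995. On these assumptions the signal shrinks but still excludes 1. Weighting would widen the intervals by an unknown amount.

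**The case against.** The strongest reply is that the definition fits its purpose. A return visit is itself care-seeking, which is what these controls are meant to pick up, so counting any code in any setting is a legitimate choice. This stands, and it is why the as-written analysis should be kept. It does not remove the difficulty that one HR then answers two questions.

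A reader might infer that carry-over claims necessarily dilute the check. The documents do not support that. Dilution needs carry-over claims to be less confounded than new episodes. The utilisation covariates in the propensity score cannot be assumed to balance one component and not the other, since prior visits also predict new care-seeking. A reader might also suppose that carry-over claims cluster just after Day 15 and so dominate the HR. The plan has no data on their timing, the Day 15 start removes the shortest follow-up, and a Cox model gives early events no special weight as such.

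Nor do the controls breach a general study standard. The 90-day COVID-19 exclusion is tied to CDC guidance on vaccination timing and is not presented as an incident-outcome rule. The influenza endpoints have no pre-index exclusion, and all-cause hospitalization has no clean window. The third control, hospitalization in Days 1 to 14, is unaffected by this point.

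Finally, the UTI and injury code lists are not in the text available, nor is Annex 2. A restriction to initial-encounter injury codes cannot be ruled out. It would reduce carry-over for injury, but a code list alone supplies no look-back rule.

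**Conclusion.** The point holds in a limited form. As far as the visible text goes, the UTI and accidental-injury controls combine prevalent and incident episodes, with no adjustment for prior UTI or injury. This can mislead the bias check in either direction. Neither direction nor size can be determined from the documents. The range shown (0.855 to 0.95 around an assumed 0.90) rests on assumed carry-over shares of 10% to 50% and on three assumed patterns of confounding. It is not evidence that the controls will falsely reassure: under the 1% incidence assumption even the diluted HR of 0.95 would still be distinguishable from 1 in both age groups of the Group 1 vs Group 2 comparison. Severity is minor, because no primary estimate changes.

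**What to change.** Keep the Table 2 definitions as they are. For each of the two controls, add a second version limited to patients with no code for that control from 90 days before index through Day 14, and count the first code after Day 14. The 365 days of prior enrolment already required make this feasible, and the window closes before follow-up opens on Day 15. Re-check covariate balance in that subset, and report both versions side by side. State the code lists and say whether injury codes are limited to initial encounters.

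Cost: 2 controls × 2 comparisons × 2 age groups = 8 extra models, assuming the controls are modelled like the other outcomes. The clean-window version will have fewer control events. Its population leaves out recent care-seekers for that condition and so differs somewhat from the cohort whose HRs it checks. That is the reason to show both: agreement suggests carry-over matters little, and disagreement tells the reader to interpret these two controls with care.

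### The Day 1-14 hospitalization negative control is computed after Day 1-14 deaths, disenrolments and COVID-19/influenza codes have been excluded, so it can understate or distort confounding and a null result is weak reassurance

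*Combined protocol and SAP*

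**What the plan says.** Section 9.2.2 applies its exclusions to the whole study: "Patients meeting any of the following criteria will not be included in the study". Two of them act on the 14 days after vaccination.

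- Exclusion 1 covers "Patients with a second dose of any type of bivalent mRNA COVID-19 or flu vaccine" in that window, and patients who "disenrolled or died within 14 days following the first dose".
- Exclusion 4 reads "Has a COVID-19 or influenza diagnosis code in any setting within 14 days after index vaccination (excluded from all cohorts").

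Table 2 in Section 9.3.2 then defines the control "Hospitalization in the 14 days following vaccination (recently vaccinated) Day 1-14", with the timing criterion "Occurs ≤14 days after the patient's first mRNA bivalent COVID-19 or influenza vaccine dose during the study period". It counts acute inpatient stays and has no diagnosis criterion. The purpose is stated: "Hospitalization in the first 14 days (ie, among recently vaccinated) uses time as a negative control", on the ground that "the vaccine likely could not biologically prevent health events until adequate levels of immunity has been achieved".

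The other two negative controls, urinary tract infection and accidental injury, are counted after Day 14. The opening of Section 9.3.2 starts every outcome at Day 15 without exception, and Sections 9.1 and 9.3.3 start follow-up and censoring after Day 14. Section 9.3.3 sets each death to the middle of its month, because Section 9.4 supplies only month and year. Section 9.7 says there is no separate SAP. Parts of Table 2 and of Section 9.7 are blacked out and Figure 1 is not shown, so the absence of a pre-exclusion cohort is a statement about the visible text only.

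**The concern.** Excluding early events suits outcomes that start on Day 15. It does not suit an outcome that lies inside the excluded window. By the plan's own argument, a group difference in admissions before immunity develops points to bias and not to vaccine effect. That argument covers COVID-19- and influenza-coded admissions and fatal admissions as much as any other, and these are the ones removed. Exclusion 4 covers any setting, so it also removes a patient admitted for another reason who had an incidental code or an outpatient code in the same fortnight.

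The control then no longer matches its counterpart, since all-cause hospitalization from Day 15 keeps coded and fatal stays. At stake is how a null result is read in an unrandomised comparison whose sample size (Section 9.5) rests on a non-inferiority margin of 1.15. The limitations in Section 9.9 do not mention the overlap.

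**Working it through.** The plan gives no event rate, power or decision rule for this control, so there is no figure to reproduce. (The 1,724 and 2,269 events in Section 9.5 do reproduce with the Schoenfeld formula, but they concern other endpoints.)

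**1. The windows side by side**

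| Item | Place | Window |
|---|---|---|
| Death, disenrolment, second dose: excluded | 9.2.2, exclusion 1 | within 14 days of first dose |
| COVID-19/influenza code, any setting: excluded | 9.2.2, exclusion 4 | within 14 days of index |
| Hospitalization: counted as negative control | 9.3.2, Table 2 | Day 1-14 |
| All-cause hospitalization: main outcome | 9.3.2, Table 2 | after Day 14 |

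The first three windows coincide. Admissions without a COVID-19/influenza code, in patients who survived and stayed enrolled, remain.

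**2. Effect on the risk ratio**

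Let f1 and f0 be the shares of Day 1-14 hospitalized patients removed by the exclusions in the Same day group and in the single-vaccine group. For rare events:

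observed RR = confounded RR × (1 − f1)/(1 − f0)

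The documents give no f values. All of those below are assumptions.

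| f1, f0 | Confounded RR 0.90 appears as | Confounded RR 0.80 appears as |
|---|---|---|
| equal, any value | 0.90 | 0.80 |
| 5%, 10% | 0.90 × 0.95/0.90 = 0.95 | 0.84 |
| 10%, 15% | 0.90 × 0.90/0.85 = 0.95 | 0.85 |
| 10%, 20% | 0.90 × 0.90/0.80 = 1.01 | 0.90 |
| 20%, 30% | 0.90 × 0.80/0.70 = 1.03 | 0.91 |
| 10%, 5% (reversed) | 0.90 × 0.90/0.95 = 0.85 | 0.76 |

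Setting the observed RR to 1 gives the f0 that hides the confounding completely: f0 = 1 − RR × (1 − f1). With f1 = 5%, this is 14.5% for RR 0.90, 24% for RR 0.80 and 33.5% for RR 0.70. Weak confounding can therefore be hidden by modest differences. Stronger confounding is weakened but stays visible unless the difference is large.

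**3. Why 0.90 is not negligible**

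|ln 0.90| / ln 1.15 = 0.105/0.140 = 0.75. A bias of that size is about three quarters of the margin on the log scale.

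**4. Precision**

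Table 5, 65+, Same day plus COVID-19 alone: 382,806 + 225,842 = 608,648, of which 62.9% are Same day. Power = Φ(|ln RR| × √(events × 0.629 × 0.371) − 1.96). The 14-day risks and the 20% loss are assumptions.

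| 14-day risk | Loss | Events | Power, RR 0.80 | Power, RR 0.90 |
|---|---|---|---|---|
| 0.5% | none | 3,043 | near 100% | 80% |
| 0.5% | 20% | 2,435 | near 100% | 71% |
| 0.2% | none | 1,217 | 96% | 43% |
| 0.2% | 20% | 974 | 92% | 36% |

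Loss of events is a smaller matter than differential removal.

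**5. Death dates**

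Section 9.3.3 states the mid-month rule for censoring. Whether exclusion 1 uses it is not stated. Assume that it does, that mid-month means the 15th, that index dates are spread evenly over 31 August 2022 to 30 January 2023, and that deaths are spread evenly over follow-up days. Then about 46% of true Day 1-14 deaths receive a date inside the window, about 30% one on or before index, and about 25% one after Day 14. About 39% of deaths dated into the window truly occur later than Day 14.

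**The case against.** The best defence is that the control should be measured in the people who are analysed. Excluded patients never enter the Day 15+ comparison, and a control run with the main cohort and its weights tests exactly that comparison. This stands as a reason to keep the present version. It does not remove the need for a second version, because the main cohort is defined by what happened during the control's own window.

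A second defence is that dropping COVID-19/influenza stays removes the vaccines' target events and so suits a negative control. The plan's own reasoning goes the other way, since before immunity develops those events are also informative about bias. A third is that two other negative controls have no window overlap. That is true, but the plan presents them mainly as markers of care-seeking. Only this control uses time, and all three are measured in the restricted cohort.

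A reader might infer more than the documents support:

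- That the control cannot show confounding at all. It counts admissions for any cause, many remain, and equal removal in both groups leaves the risk ratio unchanged.
- That the cohort is selected on the control outcome itself. Selection is on death, disenrolment, a second dose or a diagnosis code, not on hospitalization.
- That the number of lost admissions can be worked out from the 0.56% in Section 9.5. That figure is for a composite that includes ED and urgent care visits, which this control never counts.
- That everyone who died by Day 14 is removed. Month-only death dates make this inexact.

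**Conclusion.** The overlap is real on the visible text, and the control as specified may understate or distort confounding. A null result should not be read as reassurance.

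The size and direction cannot be computed from the documents. The illustration of 0.90 appearing as 0.95-1.03 rests on assumed removal shares that are 5-10 percentage points higher in the single-vaccine group. With the difference reversed, the control would exaggerate the confounding. With equal shares there is no distortion.

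The main effect estimates are untouched. What changes is the weight that this one diagnostic can bear. It is a worthwhile and cheap improvement, not a fault that invalidates the study. The Day 1-14 window also has to be reconciled with the Day 15 start for all outcomes, since no time at risk or censoring rule for this control is visible.

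**What to change.** In Table 2, specify that this control is also run in the cohort before exclusion 4 and before the death/disenrolment part of exclusion 1, with:

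- follow-up from Day 1 to Day 14;
- censoring at death, disenrolment or receipt of another vaccine;
- a stated rule for dating deaths, given month-only data;
- propensity weights estimated in that cohort.

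Show the main-cohort version beside it, so that the weights used in the main analysis are still tested. Report the number excluded on Days 1-14 by reason and by exposure group, which lets readers judge whether removal was differential. Amend Section 9.3.2 so that its Day 15 start allows for this control.

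The cost is one extra cohort flag and one model run on data already held. The downside is that the added control cohort differs slightly from the main one.
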